## Protocol Synopsis

I. Protocol title: Evaluate the efficacy of RespireAid™ in patient with externally contracted seasonal epidemic

II. Objectives: The main objective of this study is to evaluate the clinical efficacy of the RespireAid™ (Tai-wan-Qing-Guan-Yi-Hao) to ease the symptoms of fever, sore throat, and cough, and the safety after treatment.

III. Test drug
 
 
1. Name: RespireAid™ (Tai-wan-Qing-Guan-Yi-Hao) (NRICM101)
 
2. Dosage form: oral granule
 
3. Strength: 5g/sachet
 
4. Packing type: sachet
 
5. Dosage and administration: Take 1 sachet(5g) 4 times daily
 
6. Mechanism of action (if known): RespireAid™ have three targeting potential pathways in externally contracted seasonal epidemic: binding of viral spike protein to human angiotensin-converting enzyme 2 (ACE2), 3CL protease that facilitates virus replication, production of pro-inflammatory cytokines interleukin (IL)-6 and tumor necrosis factor (TNF)-α.
 

IV. Developmental phase: First in human Phase I II III IV

V. Study design:
 
 
1. Control: placebo active (please specify name and dosage) other Uncontrolled
 
2. Blinding: open label evaluator blind single blind double blind double dummy other
 
3. Randomized: yes no
 
4. Parallel Cross over Other
 
5. Duration of treatment: 5 days
 
6. Titration: forced optional none
 
7. Single national Multi center(Taiwan) Multi center
 


VI. Endpoints
 
 
1. Primary endpoint(s): Efficacy endpoint 
 
• Time to symptom-free for fever.
 
 
 

Safety endpoint

- Treatment-emergent adverse events (TEAEs)

## 2. Secondary endpoints:

Efficacy endpoint

- Time to symptom-free for sore throat.
- The change from baseline in the severity of cough during treatment period.

Safety endpoint

- Physical examination
- Vital sign

## VII. Selection criteria

## 1. Main inclusion criteria:

- (1) Male or unpregnant female patients  $\geq 18$  years to  $\leq 79$  years of age, who have the symptoms of fever, sore throat, and cough (match the definition in table 1 to 2 in protocol), by investigator's judgement, with mild to severe symptoms ( $> 20$  mm in each VAS).
- (2) With BMI between 18 to 30 kg/m^2.
- (3) Without a history for alcohol or drug abuse, or other significant organic diseases.
- (4) No history of cancer. Unless no signs of relapse occurred for over 5 years which no anticancer therapies are needed.
- (5) Ability to read and write Chinese, and provide data through questionnaire.
- (6) Ability to understand and comply all procedures of the study, and provide written consent.

## 2. Main exclusion criteria:

- (1) Confirmed diagnosis of pneumonia or other disease by chest X ray which would impact on study evaluations.
- (2) Must require long-term use of NASIDs, corticosteroids or other immunosuppressive agents.
- (3) Pregnant female.
- (4) Subjects are not suitable for the conduct of the study for any other reasons, determined by the investigator. For example, subjects who require to use antibiotics, COVID-19 or influenza antiviral drugs.

## VIII. Study procedures:

This is a multicenter, parallel, double-blind, randomized, placebo-controlled study. A total of 258 male or unpregnant female outpatient subjects  $\geq 18$  years to  $\leq 79$  years of age will be enrolled into this study (dropout rate 10%). There will be 2 visits in this study. In Visit 1 (Day 1), subjects who have the symptoms of fever, sore throat, and cough (match the definition in table 1 to 3 in protocol), by investigator's judgement will be recruited into the study.

Subjects will be randomized into the RespireAid™ group or placebo group with allocation rate 2:1.

Following to the clinical guideline of NRICM101, subjects in RespireAid™ group will take drug four times daily with 20g oral granule, administered for 5 days. The subjects in placebo group received study drug with the same dose frequency. Other than study drugs, the rescue drug, acetaminophen, will be administered. If subjects have moderate or severe fever, sore throat, he/she could receive one rescue medication (500mg) per 4 hours, up to 6 tablets in total in one day. Subjects will be educated how to use e-dairy. The dairy will be recorded the severity of fever, sore throat, and cough from baseline (Day 1, before use of study drug) to Day 5. The efficacy endpoint will be the improvement of fever, sore throat, and cough, and the safety endpoint will be adverse events after treatment. The study and rescue drugs will be dispensed to subjects and the study staff will teach them how to receive medications. If subjects have persistent fever, unscheduled visits will be arranged to check whether or not they would be suitable to participate into this study. Adverse events will be recorded at Visit 2(Day 8), and the dairy with drug record will be checked.

IX. Concomitant treatment:

1. During study period, the drugs which may impact the efficacy evaluation (i.e. fever, sore throat, and cough) will be prohibited, including
  - (1) Chinese medication other than study drug
  - (2) Western medication other than study drug
    - NSAIDs
    - Acetaminophen
  - (3) Expectorant cough medicines
    - Mucolytics, such as Bromhexine
    - Antitussives, including Opioids (e.g. Codeine, Ethylmorphine, Pholcodine), nonopioids (e.g. Noscapine, Dextromethorphan, Chlophedianol), antihistaminics and Prenoxdiazine
    - Adjuvant antitussives, such as bronchodilators
2. During study period, long-term use of NASIDs, corticosteroids or other immunosuppressive agents will be prohibited.
3. During study period, antibiotics, COVID-19 or influenza antiviral drugs will be prohibited.
4. During study period, subject could receive other treatments/therapies that are not otherwise prohibited and, in the judgment of the Investigator, are required for proper medical care.

X. Statistics

- 1. Primary hypothesis:  superiority  non inferiority  
 equivalence  other
- 2. Sample size: enrolled 258 subjects  
 evaluable 231 subjects
- 3. Efficacy population:  ITT  PP  other  
 Safety population:  ITT  PP  other: Safety Population
- 4. Statistical method(s) for efficacy/safety evaluations:

Efficacy Evaluation

The primary efficacy endpoint is the “time to symptom-free for fever” which is the days of the symptom-free for fever based on the diary record. The primary endpoint will be analyzed by weighted log-rank test for comparison between RespireAid™ and placebo groups. Kaplan-Meier plot will be drew to present the time to event data. The secondary efficacy endpoint of the “time to symptom-free for sore throat” will be analyzed as the analysis of the primary efficacy endpoint. The change from baseline in the severity of cough during treatment period will be summarized as categorical data with frequency and percentage and analyzed by Chi-square test.

Safety Evaluation

All safety assessments, including AEs, physical examinations (PEs), and vital signs (VS), where indicated, will be presented using descriptive statistics by study groups and time points.

- 5. Planned interim analysis:  yes  no

XI. Please attach flow chart and/or assessment schedule, if available.

Visit	1	2
	Screening/Strat of Treatment	End of Treatment/End of Study/Early withdrawal
Days	1	8
Windows		±2
Informed Consent	X	
Inclusion/Exclusion criteria	X	
Randomization	X	
Medical History	X	
Demographic data	X	
Physical Examination	X	X
Vital Signs	X	X
COVID-19 testing		
Chest X ray	X	
Urine Pregnancy test a	X	
Dispense study drug b	X	

Dispense rescue drug c	X	
Return study drug		X
Return rescue drug		X
e-diary d	X	X
Concomitant Medication	X	X
TEAE	X	X

a: If the result of urine pregnancy test is positive, the subject won't be enrolled into the study.
 
b: The study drugs will be given four times daily with 20g oral granule, administered for 5 days.
 
c: The rescue drugs could be given one tablet (500mg) per 4 hours, up to 6 tablets in total in one day.
 
d: E-Dairy card will be recorded before use of study drugs(baseline), Day 1 to Day 5.

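### Do the protocol's three statements of the study-drug dose differ fourfold?

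*Protocol*

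**What the plan says.** The regimen is stated in three places in the protocol.

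- **Section III (Test drug).** The product is an oral granule, "Strength: 5g/sachet", and the dosage line reads "Take 1 sachet(5g) 4 times daily".
- **Section VIII (Study procedures).** Subjects in the active arm "will take drug four times daily with 20g oral granule, administered for 5 days".
- **Section XI (assessment schedule), footnote b**, which is attached to dispensing at Visit 1: "The study drugs will be given four times daily with 20g oral granule, administered for 5 days".

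Section V gives the length of the course: "Duration of treatment: 5 days". For the control arm, Section VIII says only "The subjects in placebo group received study drug with the same dose frequency" and gives no amount in grams.

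**The concern.** In Section III the amount beside the frequency is 5 g, and it is plainly the amount per intake because it is tied to one sachet. In Section VIII and footnote b the amount beside the same frequency is 20 g, with nothing to mark it as per intake, per day or in total. A reader who carries the Section III construction over to the other two places would take 20 g as the amount at each of four intakes, which is four times as much.

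If sites did read it both ways, the consequences would be real. Exposure would differ between sites, some patients would take far more than others, and adverse events, a primary safety endpoint, would not refer to one regimen. The design leaves little chance to catch such an error during treatment. Drug is dispensed and its use is taught at Visit 1, and the next scheduled visit is Day 8 (±2 days), after the 5-day course. The placebo text fixes only the frequency, so it does not settle the reading.

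**Working it through.** **Inputs.** Sachet strength 5 g (Section III); one sachet per intake, four intakes a day (Section III); 20 g with four intakes a day, unlabelled (Section VIII and footnote b); 5 days of treatment (Section V, repeated in Section VIII and footnote b).

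**Formulas.** Daily amount = amount per intake × intakes per day. Course amount = daily amount × 5 days. Sachets = amount ÷ 5 g.

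**Step 1: Section III alone.** 5 g × 4 = 20 g a day. Over the course, 20 g × 5 = 100 g, or 4 × 5 = 20 sachets. The 20 g printed in Section VIII and footnote b is reproduced exactly as a daily total.

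**Step 2: the two readings of the unlabelled 20 g.**

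| Reading of 20 g | Per intake | Per day | Course | Sachets per intake | Sachets per course | Ratio to Section III |
|---|---|---|---|---|---|---|
| Daily total | 20 ÷ 4 = 5 g | 20 g | 100 g | 1 | 20 | 20 ÷ 20 = 1 |
| Amount at each intake | 20 g | 20 × 4 = 80 g | 400 g | 20 ÷ 5 = 4 | 80 | 80 ÷ 20 = 4 |

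**Step 3: what each reading requires of the text.** The daily-total reading leaves every printed figure standing: sachet strength, one sachet per intake, four intakes, 20 g and 5 days. The per-intake reading adds a qualifier that neither Section VIII nor footnote b contains. It also needs four sachets at each intake and 16 a day, which conflicts with the explicit one-sachet instruction in the field that exists to state the dosage. The only presentation described is a 5 g sachet; no 20 g unit appears.

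**Step 4: accountability.** Section III with the 5-day course implies 20 sachets per subject, so the drug return and diary check at Visit 2 do have a target, although footnote b does not print it.

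**The case for a change.** The best case for a change is that the loose wording sits in the two places staff work from: the procedures section and the footnote tied to dispensing. The protocol also shows that it can be explicit. For the rescue drug, Section VIII and footnote c give both a unit amount (one 500 mg tablet per 4 hours) and a daily cap (6 tablets), and footnote c stands directly below footnote b. In a multicentre outpatient trial with two visits, a misreading might not be noticed until the course is over. Section VIII also defers to a clinical guideline for the drug that the document does not reproduce. A dose statement belongs in the protocol and cannot be left to a statistical analysis plan, and labelling the amount would cost almost nothing.

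Part of this stands. The 20 g is unlabelled, the contrast with the rescue-drug text is fair, and a label would read better. The step from there to a fourfold discrepancy does not stand. It needs sites to override the dosing field with a figure that, as a daily total, agrees with that field to the gram, and nothing in the document suggests they would. Section VIII has staff teach subjects how to take the medication and has the diary with the drug record checked at Visit 2. The supplied text is headed as a synopsis and refers to tables in the protocol that are not shown, so it cannot be inferred that sites lack a fuller dispensing instruction.

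**Conclusion.** No contradiction is established. The three statements agree exactly (ratio 1) with 20 g as the daily total. The ratio of 4 comes only from a reading that the text does not state and that conflicts with Section III. What is left is a missing qualifier in two places, a clerical slip that staff can resolve from the dosing field of the same document.

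Following the plan as written gives the same regimen with or without the label. Sample size (258 enrolled, 231 evaluable), power, the endpoints and the analysis are unaffected. The sponsor may reasonably label the amount as per intake or per day when the text is next edited, so that the three places read alike, but no result or conclusion depends on it.

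This rests on two assumptions: that the dosage line in Section III is read together with Section VIII and footnote b, and that no site document outside the supplied text says otherwise. It is a judgement on whether the figures are consistent. Which dose applies is for the sponsor to confirm, and none is proposed here.

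### The suitability check for persistent fever falls after randomisation and is triggered by absence of the primary event; one clause should keep the fever diary running to Day 5 whatever that check decides

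*Protocol*

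**What the plan says.** Section VIII (Study procedures) first describes randomisation, dosing, diary training and dispensing, and then states: "If subjects have persistent fever, unscheduled visits will be arranged to check whether or not they would be suitable to participate into this study". The same section says "There will be 2 visits in this study". In the Section XI schedule, the Day 1 column is headed "Screening/Strat of Treatment" and carries the eligibility criteria, randomisation and dispensing together. The other column is Day 8 ±2, which also serves as the early-withdrawal visit.

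Note d to the schedule gives the diary rule: "E-Dairy card will be recorded before use of study drugs(baseline), Day 1 to Day 5". Section VIII says the same, without exceptions.

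The primary endpoint is the time until the diary shows freedom from fever. Section X states: "The primary endpoint will be analyzed by weighted log-rank test for comparison between" the two groups.

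Exclusion criterion 4 (Section VII) leaves suitability to the investigator and illustrates it thus: "For example, subjects who require to use antibiotics, COVID-19 or influenza antiviral drugs". Section IX, item 3 adds: "During study period, antibiotics, COVID-19 or influenza antiviral drugs will be prohibited".

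**The concern.** An eligibility question is put to people who have already been randomised. What triggers it is an outcome: a subject with persistent fever is one who has not yet had the primary event. A drug that works would make the trigger more frequent on placebo.

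The sentence attaches no day to persistence, so the check can fall inside the five diary days. It also does not say what happens to the diary of a subject found unsuitable. If that subject leaves the study, the remaining fever entries are never made, and no later analysis rule can restore them.

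Kaplan-Meier estimation and the log-rank test treat a censored subject as having the same outlook as those still under observation. That fails if, among equally febrile subjects, the sicker ones are removed. The protocol's own example of unsuitability, needing drugs that are prohibited on study, points towards that kind of selection.

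**Working it through.** **Plan's own figure.** 231/(1 − 0.10) = 256.7, so 257. Rounded by arm at 2:1: 154/0.9 = 171.1, so 172; 77/0.9 = 85.6, so 86; total 258, as stated. The 231 cannot be re-derived, because the protocol text gives no alpha, power or effect size.

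**Order of events.** Eligibility and randomisation are on Day 1, the diary runs from baseline to Day 5, and the next scheduled visit is Day 8. An unscheduled visit for fever that has persisted therefore falls after randomisation. If it falls on or after Day 5, no primary-endpoint entry is at risk.

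**Assumed inputs (none is in the protocol).** In the base case 40% of subjects are slow resolvers, with a daily resolution probability of 0.25 on active and 0.10 on placebo; the rest resolve at 0.45 per day in both arms. Leaving is 10% pooled (26 of 258, the whole dropout allowance, so an upper case). Only febrile slow resolvers leave, and they are censored. Fever is assumed to resolve at the same rate after leaving.

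**Bias, closed form.** Let a be the slow daily probability, s_k = 0.4(1 − a)^k and f_k = 0.6(0.55)^k. With full follow-up the proportion still febrile at Day 5 is s_5 + f_5:
- active: 0.4(0.75^5) + 0.6(0.55^5) = 0.0949 + 0.0302 = 0.125, so 87.5% fever-free
- placebo: 0.4(0.90^5) + 0.6(0.55^5) = 0.2362 + 0.0302 = 0.266, so 73.4% fever-free

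If a share w of febrile slow resolvers is censored after Day k, Kaplan-Meier instead estimates (s_k + f_k) × [(1 − w)s_5 + f_5] / [(1 − w)s_k + f_k].

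For k = 3, s_3 is 0.1688 on active and 0.2916 on placebo, and f_3 is 0.0998. The pooled 10% requires w = 0.10 / [(2 × 0.1688 + 0.2916)/3] = 0.10/0.2097 = 0.477. Then:
- active: 0.2686 × 0.0798/0.1881 = 0.114, so 88.6% (+1.1 points)
- placebo: 0.3914 × 0.1537/0.2523 = 0.238, so 76.2% (+2.8 points)

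The same steps give 88.8%/76.7% after Day 2 (+1.3/+3.4) and 88.2%/75.1% after Day 4 (+0.75/+1.8). If leaving is not selective, 1 − w multiplies both s and f and cancels, so there is no bias.

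**Power.** Simulated with an unweighted log-rank test (the protocol does not state the weights), two-sided 5%. The comparator is 231 subjects followed completely, because the plan already allows for 10% dropout.

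| Assumed pattern, 10% leaving selectively | 258 all followed | 231 all followed | 258 with leavers censored | Change against 231 |
|---|---|---|---|---|
| Base, after Day 2 | 71.3% | 66.7% | 57.7% | −9.0 |
| Base, after Day 3 | 70.9% | 66.7% | 60.7% | −6.0 |
| Base, after Day 4 | 70.7% | 66.7% | 65.6% | −1.1 |
| Uniform hazard ratio 1.5, after Day 3 | 47.1% | 43.1% | 46.4% | +3.3 |
| Benefit in fast resolvers only, after Day 3 | 35.7% | 33.0% | 38.3% | +5.3 |

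A repeat of the base case gave 66% for 231 followed completely, and 57%, 61% and 66% with censoring after Days 2, 3 and 4: losses of 9, 5 and 0. Non-selective leaving after Day 3 in the base case gives 64.7%, about 2 points below 66.7%. Selective leaving of 5% after Day 3 gives 66.9%, no loss.

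**Type I error.** With no treatment effect and the same rule in both arms, rejection was 5.3% both with full follow-up and with censoring.

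**The case against.** The strongest reply is that the sentence orders a check and nothing more. It states no withdrawal, no end to the diary and no exclusion from analysis, and the only diary rule in the text runs to Day 5 without exception. This stands: a reader might infer that febrile subjects are to be withdrawn, and the document does not say so. What remains is that nothing says the diary rule survives a finding of unsuitability, and ending participation is a natural consequence of such a finding.

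Second, this is a synopsis that refers to tables in a fuller protocol, and that fuller text may already keep these subjects in follow-up. If so, only this sentence needs aligning. The boxes for the efficacy population cannot be read in the available text, so retention as randomised may already be settled. Censoring rules and sensitivity analyses can sit in the SAP. A SAP cannot supply diary entries that were never collected, however.

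Third, a reader might take the base-case fall after Day 3, from about 71% to about 61%, as a 10-point loss of power. That compares with 258 subjects and no dropout at all, which the plan never assumed. Against 231 evaluable, the loss is 5 to 6 points. The base case is also the pattern in which slow resolvers alone benefit, and the other two patterns show no loss.

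Fourth, deciding what to do about a febrile outpatient is clinical management. That stands, so the visit and its decision should not be rewritten. Only the data collection that follows is a statistical matter.

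**Conclusion.** The point holds as a cheap improvement. Randomised subjects who have not had the primary event are sent to a check of their suitability for the study, and the text does not secure their diary afterwards. Loss of data is possible, not stated.

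If about 10% leave selectively, the Day 5 fever-free proportion is overstated by roughly 1 to 3.5 points per arm. Base-case power falls by about 9, 5 to 6, or 0 to 1 points for a check after Day 2, 3 or 4. These figures rest on assumed resolution rates, trigger day, share leaving and degree of selection. If leaving is not selective there is no bias, only some loss of late information. The direction of the effect on power cannot be settled from the document.

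A reader might also infer an inflated false-positive rate. The calculations do not support that when the rule is applied equally in both arms. The case for the change is that lost entries cannot be recovered and keeping them costs little; no large bias has been shown.

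**What to change.** Leave the unscheduled visit and its clinical decision as they are. Add one clause to Section VIII: a randomised subject who stops study drug or starts a prohibited treatment after such a visit is still asked to complete the existing e-diary to Day 5 and remains in the randomised set. Reconcile the sentence's wording about suitability with that clause, so that the check is not read as ending follow-up. Report such cases by arm.

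A sensitivity analysis counting subjects with no further diary data as not fever-free is optional and can be left to the SAP.

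The cost is one clause and one to three more diary days (for a check after Day 4, 3 or 2) in a few subjects who already hold the e-diary, at most 26 of 258 if all planned dropout came from this cause. The downside is that entries made after a prohibited treatment reflect that treatment, so they need a flag.

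### No adverse-event capture is scheduled between Day 1 and Visit 2 (Day 8 ±2), although treatment-emergent adverse events are a primary endpoint and an e-diary already runs on every dosing day

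*Protocol*

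**What the plan says.** Section VI of the Protocol lists TEAEs under the primary endpoints, as the safety endpoint. Section V gives "Duration of treatment: 5 days". Section VIII states "There will be 2 visits in this study" and, on adverse events, "Adverse events will be recorded at Visit 2(Day 8), and the dairy with drug record will be checked".

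The section XI schedule gives Visit 2 a window of ±2 days around Day 8 and labels it "End of Treatment/End of Study/Early withdrawal". Its TEAE row is marked at both Visit 1 and Visit 2, whereas section VIII names Visit 2 only.

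On the diary, section VIII says "The dairy will be recorded the severity of fever, sore throat, and cough from baseline (Day 1, before use of study drug) to Day 5", and footnote d of the schedule says "E-Dairy card will be recorded before use of study drugs(baseline), Day 1 to Day 5". A drug record is checked together with the diary. Adverse events are not named as diary content.

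The one contact described outside the two visits is this: "If subjects have persistent fever, unscheduled visits will be arranged to check whether or not they would be suitable to participate into this study".

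**The concern.** The efficacy symptoms are recorded daily, but the primary safety endpoint has one useful scheduled collection point after dosing starts, and for subjects who complete treatment that point lies after dosing has ended. An event that is mild and over within a day is the kind most easily forgotten, or assigned to the wrong day, when it is first recorded several days later.

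Section X says that safety data will be summarised descriptively by group and time point. With no formal test planned there, the observed rates and their timing are the safety result. If events are lost, the absolute rates and the difference between arms shrink. If onset days are blurred, the relation of an event to study drug or to rescue acetaminophen is harder to judge. The instrument that could fix onset to the day is already in the subject's hands.

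**Working it through.** **Timing.** Inputs: dosing on Day 1 to Day 5 (section V, and the Day 1 pre-dose baseline in section VIII); Visit 2 at Day 8 ±2 (section XI), so Day 8 − 2 = Day 6 to Day 8 + 2 = Day 10. The gap between an event and its scheduled recording is the visit day minus the event day.

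| Visit 2 held on | Gap for a Day 1 event | Gap for a Day 5 event |
|---|---|---|
| Day 6 | 6 − 1 = 5 days | 6 − 5 = 1 day |
| Day 8 | 8 − 1 = 7 days | 8 − 5 = 3 days |
| Day 10 | 10 − 1 = 9 days | 10 − 5 = 5 days |

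For a subject who completes treatment, the visit falls after Day 5 throughout the window.

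**Visit 1.** The schedule also marks TEAE here. Visit 1 is the day of consent, screening, randomization and dispensing, so it precedes or coincides with the first dose and can contribute few treatment-emergent events. The mark does not close the gap, but it does differ from section VIII.

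**Arm sizes.** The plan's enrolled total can be reproduced: 231 / (1 − 0.10) = 256.7, so 257, and the next multiple of 3 for 2:1 allocation is 258. That gives 258 × 2/3 = 172 on RespireAid and 258 / 3 = 86 on placebo. The point does not depend on this figure; it only supplies denominators for the illustration.

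**Illustration, on assumptions only.** The document gives no TEAE rate and no capture rate. Suppose that the same share of subjects with events is captured in both arms. The expected count is arm size × true rate × capture.

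| Assumed true rates | Capture | RespireAid (of 172) | Placebo (of 86) | Observed difference |
|---|---|---|---|---|
| 20% vs 10% | 100% | 34.4 | 8.6 | 10 points |
| 20% vs 10% | 80% | 27.5 | 6.9 | 8 points |
| 20% vs 10% | 60% | 20.6 | 5.2 | 6 points |
| 30% vs 15% | 100% | 51.6 | 12.9 | 15 points |
| 30% vs 15% | 80% | 41.3 | 10.3 | 12 points |
| 30% vs 15% | 60% | 31.0 | 7.7 | 9 points |

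Equal under-capture leaves the ratio of the true rates at 2 and shrinks the absolute rates and the difference in proportion. The table applies one capture rate to all TEAEs. If only mild events are lost, the effect is smaller.

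**The case against.** The strongest reply is that this text is a synopsis. It refers to tables in a fuller protocol that is not shown, and spontaneous or serious-event reporting may be described there. Section VIII says when adverse events are recorded, not how they are elicited. Both arms are blinded and assessed alike. One adverse-event assessment a nominal three days after a 5-day course is a design choice, not an error.

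Much of this stands, and it rules out three stronger readings that a reader might infer:

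- **That all TEAEs are taken by recall.** No elicitation method is stated, and a subject may report an event earlier or keep a note of it.
- **That events are under-counted as a matter of fact.** No figure in the document shows or sizes a loss.
- **That nothing can be acted on during treatment.** Visit 2 doubles as the early-withdrawal visit, so a subject who stops early can be assessed then. Section IX, item 4 allows treatment that the investigator judges necessary, which presupposes that problems can come to notice. Unscheduled visits exist, though the stated trigger is persistent fever and the stated purpose is to check suitability for the study.

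What the reply does not remove is the text itself. The recording time and the diary content are both stated, so the point does not rest on silence alone. Blinding and equal assessment protect the ratio, but not the absolute rates or the onset dates.

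**Conclusion.** The point holds as a limited one. The synopsis schedules no adverse-event capture between Day 1 and Visit 2, which falls 1 to 5 days after the last dosing day and 5 to 9 days after the first. The daily diary is not described as filling that gap. For subjects who complete treatment, mild, short-lived events may be missed or misdated.

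The timing follows directly from the document. The amount of any loss does not: the tabulated 20% to 40% shrinkage of the difference only restates the assumed 80% and 60% capture. The conclusion also assumes that the fuller protocol adds no scheduled capture in this interval. Separately, and without any assumption, section VIII and the section XI schedule differ on when TEAEs are assessed. This is an inexpensive improvement to a primary endpoint, and it does not show that the planned safety analysis is invalid.

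**What to change.** 1. Add one item to the existing e-diary for Day 1 to Day 5, asking whether the subject had any new or worse health problem that day other than fever, sore throat or cough, with space to describe it.
2. At the diary check already planned for Visit 2, confirm and complete these entries and ask about events since Day 5.
3. Reword the section VIII sentence to say that adverse events are collected daily in the e-diary and confirmed at Visit 2.
4. Reconcile that sentence with the section XI schedule, which marks TEAE at both visits, and state what the Visit 1 mark is meant to capture. Add the new item to footnote d.

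The cost is one diary question, the wording changes, and more minor events to confirm and code. The reported TEAE rate is likely to be somewhat higher in both arms. No extra visit is needed. The fix does not depend on daily review of entries by the site; the document describes no such review, and adding one would be new work.

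### The primary weighted log-rank test ignores the pre-dose fever severity already recorded; stratifying by it is an optional, low-cost gain in efficiency, not the correction of an error

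*Protocol*

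**What the plan says.** **Test.** In X. Statistics, item 4, the primary endpoint is time to symptom-free for fever, "which is the days of the symptom-free for fever based on the diary record". For the test: "The primary endpoint will be analyzed by weighted log-rank test for comparison between" the RespireAid and placebo groups, with a Kaplan-Meier plot. No stratum, covariate or weight function is named. Time to symptom-free for sore throat "will be analyzed as the analysis of the primary efficacy endpoint".

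**Patients.** VII. Selection criteria, inclusion (1), admits patients "with mild to severe symptoms", so baseline severity will vary.

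**Baseline record.** VIII. Study procedures: "The dairy will be recorded the severity of fever, sore throat, and cough from baseline", meaning Day 1 before study drug. Footnote d of the schedule in XI agrees: "E-Dairy card will be recorded before use of study drugs(baseline), Day 1 to Day 5". Section VIII also uses severity grades when it describes access to rescue medication: "If subjects have moderate or severe fever, sore throat".

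**Randomisation and size.** Section VIII gives 2:1 allocation and no stratification factor. X. Statistics, item 2, gives 258 enrolled and "evaluable 231 subjects". The only use of baseline severity in the analysis text is the change in cough, a secondary endpoint.

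**The concern.** The endpoint is the time until a graded symptom has gone. It is plausible, though the Protocol does not quantify it, that patients who start with more severe fever take longer to become free of it. If so, pooling all grades in one log-rank comparison mixes fast and slow resolvers. A given within-severity treatment effect then appears diluted, and power falls. A stratified test compares patients only with others of the same starting grade and avoids that loss.

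What is at stake is power in the primary efficacy test, not its validity. Randomisation covers chance imbalance in severity. The choice is also time-sensitive: stratification chosen after unblinding would be a data-driven analysis.

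**Working it through.** **1. The plan's own figure.** At 2:1, 231 evaluable subjects give 231 × 2/3 = 154 and 231 × 1/3 = 77. Inflating each arm for 10% dropout gives 154/0.9 = 171.1, rounded up to 172, and 77/0.9 = 85.6, rounded up to 86. The total is 258, as stated. The 231 cannot be rebuilt, because the text shown gives no alpha, power, effect size or event rate.

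**2. The two tests.** At each diary day *j* in stratum *s*, let *n* be the number at risk (*n*₁ active, *n*₀ placebo), *d* the number resolving (*d*₁ active) and *w* the weight.

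- Z = Σₛ Σⱼ w (d₁ − n₁d/n) / √[Σₛ Σⱼ w² V]
- V = n₁n₀d(n − d) / [n²(n − 1)]

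The unstratified test treats everyone as one stratum. The stratified test sums over baseline grades.

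**3. Simulation A.** Taken from the Protocol: 154 vs 77 and diary records to Day 5. Assumed, because the Protocol does not give them:

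- within-severity hazard ratio 1.5, two-sided 5%;
- placebo resolution of 25% or 35% per day in the middle grade;
- mild/moderate/severe mixes of equal thirds, 60/30/10, 15/70/15 and 10/30/60;
- a constant factor on the daily resolution hazard per severity step. From severe to mild, factor 0.8 means a hazard ratio of 1/0.8² = 1.6, factor 0.67 means 1/0.67² = 2.2, and factor 0.5 means 1/0.5² = 4.

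There were 4,000 replicates per cell under the effect and 8,000 under the null. The standard error of one power figure near 0.7 is √(0.7 × 0.3/4000), or 0.7 points.

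Power with equal thirds and 25% per day, unstratified vs stratified:

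| Factor per step | Log-rank | Gehan-weighted |
|---|---|---|
| 1.0 (not prognostic) | 0.737 vs 0.734 | 0.671 vs 0.667 |
| 0.8 (weak) | 0.714 vs 0.727 | 0.661 vs 0.663 |
| 0.67 (moderate) | 0.675 vs 0.734 | 0.630 vs 0.664 |
| 0.5 (strong) | 0.575 vs 0.718 | 0.554 vs 0.661 |

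Power change in points over all mixes and both resolution rates (small differences from the table are rounding):

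| Factor per step | Log-rank | Gehan-weighted |
|---|---|---|
| 1.0 | -1.4 to -0.3 | -0.8 to -0.2 |
| 0.8 | -0.3 to +1.2 | -0.5 to +1.0 |
| 0.67 | +1.2 to +5.8 | +0.8 to +3.8 |
| 0.5 | +5.9 to +14.3 | +4.1 to +10.7 |

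The largest gains need equal thirds or, for the log-rank only, a mostly mild mix. The smallest gain at factor 0.5 comes from 15/70/15 at 25% per day: log-rank 0.669 vs 0.728, Gehan 0.624 vs 0.665.

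**4. Type I error.** Over the null cells it is 4.4% to 5.7% unstratified and 4.5% to 5.5% stratified. The means over 24 cells are 0.050 vs 0.051 for both the log-rank and the Gehan test.

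**5. Simulation B, different assumptions.** Hazard ratio 1.5 or 1.6, mixes 35/45/20 or 60/30/10, placebo middle-grade hazard 0.35 or 0.6 per day, Fleming-Harrington(1,0) as the weighted version, 8,000 replicates. Power change in points:

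| Factor per step | Log-rank | Fleming-Harrington(1,0) |
|---|---|---|
| 1.0 | -1.1 to -0.3 | -0.8 to -0.3 |
| 0.7 | +1.8 to +3.5 | +1.4 to +2.8 |
| 0.5 | +11.2 to +14.3 | +7.1 to +9.7 |

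Type I error was 0.045 to 0.055 for every test. A further independent run at 154 vs 77 and hazard ratio 1.5 gave losses of 0.4 to 1.7 points at factor 1.0, and gains of about 1 to 5 at 0.67 and 3 to 14 at 0.5. The pattern is the same throughout.

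**The case against.** The strongest objection is that nothing here is wrong. The stated test is valid, strata are routine SAP content, the SAP is not shown, and a stratified weighted log-rank test is still a weighted log-rank test. All of that stands, and it is why the point is an optional improvement and not an omission. It does not remove the point: the Protocol states a primary test, and a concrete, probably better version of that test uses data already collected. If the SAP already stratifies, nothing more is needed.

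The benefit also rests on assumptions. Hazard ratio, severity mix, prognostic gradient and weight are all supplied here. The large gains need a fourfold mild-to-severe difference in resolution hazard, which nothing in the Protocol supports. Rescue acetaminophen, available for moderate or severe fever, could flatten the gradient. Rescue use was not simulated; if it brought the gradient down to about 0.8, the gain would be close to nil. This stands too, so the upper figures should not be read as expected values.

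The power comparison holds the within-severity effect fixed. If the 231 were sized on a pooled effect, planned power is unaffected and any gain is a bonus.

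Strata could be thin: a grade with a 10% share would hold about 8 of 77 placebo subjects (0.10 × 77 = 7.7). The 60/30/10 and 10/30/60 mixes cover this, and the largest loss in simulation A is still 1.4 points.

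**Conclusion.** The point holds as a cheap efficiency improvement. The stated primary test makes no use of the pre-dose severity record, and neither the stated randomisation nor the rest of the primary analysis does. The test controls type I error and needs no correction.

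The trade-off is lopsided. About 1 point of power is at risk if severity is not prognostic (1.7 at most in any run). Against that stands roughly nothing if it is weakly prognostic, about 1 to 6 points if moderately so, and about 3 to 14 if strongly so, with smaller maxima for the weighted versions tried. This rests on the assumed within-severity hazard ratio (1.5, or 1.6 in part of simulation B), on proportional hazards within grade, and on a severity mix and gradient that the Protocol does not give. Confidence in the size of the gain is therefore only medium. Stratifying also changes the comparison from a marginal to a within-severity one.

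**What to change.** Add one sentence, in the protocol or the SAP, before unblinding:

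> The weighted log-rank test for the fever endpoint is stratified by baseline fever severity grade (mild, moderate, severe) from the pre-dose diary record; the test for the sore-throat endpoint is stratified by baseline sore-throat severity grade.

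No new data, visits or subjects are needed. Entry is judged on a VAS, and the text shown does not name the diary's severity scale. If the diary holds a score and not a grade, fix the cut-points in the same sentence. Keep the strata few, given about 77 evaluable placebo subjects. The cost is about 1 point of power if baseline severity turns out not to be prognostic.
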